6.6.5. Dose Modification for Selpercatinib Interstitial Lung Disease/Pneumonitis

For Grade 2, withhold selpercatinib until resolution. Resume at next lower dose. Discontinue selpercatinib for recurrent ILD/pneumonitis.

For Grade 3 or 4, discontinue selpercatinib.

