- Dose modifications for ECG changes are described in Section 8.2.1. If a patient receiving selpercatinib or cabozantinib experiences QTcF > 500 msec despite 2 dose reductions and if the investigator deems it in the best interest of the patient, the patient may continue treatment with study drug with Lilly medical approval. In addition, Lilly will request a copy of the ECGs for adjudication.
- Upon resolution (or return to patient's baseline) of AEs at least possibly related to treatment, reduce the dose as follows:
 - If previously receiving dose level 1, resume treatment at dose level -1
 - If previous receiving dose level -1, resume treatment at dose level -2
 - If previously receiving dose level -2, resume treatment at the same dose level. If a second AE requiring dose modification occurs at dose level -2, discontinue study treatment.
 - For AEs clearly unrelated to study treatment that resolve or return to patient's baseline in ≤ 14 days, dose reduction is not required.
 - Re-escalation to a prior dose level after a dose reduction is permitted once the AE requiring dose reduction is resolved. See Sections 6.6.1 through 6.6.4 and the IB for specific dose adjustments required for patients receiving selpercatinib.
 - Above are guidelines and may be superseded by local practice guidelines or advice per the local cabozantinib/vandetanib labels when appropriate.

Except as noted, a maximum of 2 dose level reductions will be allowed. Any patient requiring > 42 days omission of treatment for drug-related toxicities will meet the criteria for study treatment discontinuation. Treatment omissions of > 42 days in extenuating circumstances that are not drug-related (e.g. recovery from motor vehicle accident) may be approved by the Lilly medical team.

General Dose Reductions for Treatment Related Toxicities^a

| Dose Level | Time | Selpercatinib Dose (mg) | Cabozantinib Dose (mg) ^b | Vandetanib Dose (mg) |
|---------------|------|-------------------------|-------------------------------------|----------------------|
| Dose Level 1 | AM | 160 | 140 | 300 |
| | PM | 160 | - | - |
| Dose Level -1 | AM | 120 | 100 | 200 |
| | PM | 120 | - | - |
| Dose Level -2 | AM | 80 | 60 | 100 |
| | PM | 80 | - | - |

^a Unless other specific dose reductions, as per Sections 6.6.1, 6.6.2, 6.6.3, and 6.6.4.

In the instance that vandetanib 100-mg tablets are unavailable, but vandetanib 300-mg tablets are available, the below table is to be followed in adult patients.

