6.6.1. Dose Modifications for Selpercatinib Hypersensitivity

If selpercatinib drug hypersensitivity is suspected, study drug should be held and treatment with steroids at 1 mg/kg prednisone (or equivalent) should be initiated. Upon resolution, selpercatinib may be resumed at a reduced dose of 40 mg BID (or adolescent equivalent dose) while continuing steroids at the same dose. Note that this dose reduction does not require sponsor approval. Hypersensitivity has recurred in some patients, typically at 3 to 6 hours following drug administration.

Discontinue selpercatinib for recurrent clinically significant hypersensitivity. In the absence of clinically significant recurrent drug hypersensitivity, the dose of selpercatinib may be escalated sequentially to 80 mg BID, 120 mg BID, and 160 mg BID (or adolescent equivalent doses) for a minimum of 7 days at each dose. Once the patient has tolerated treatment for a minimum of 7 days at the final dose, steroids may be tapered slowly.

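### After a first Grade 2 ILD/pneumonitis event on selpercatinib 80 mg BID, Protocol Section 6.6.5 orders a lower dose, while Section 6.6 defines none and orders the same dose

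*Protocol*

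**What the plan says.** Protocol Section 6.6.5, which amendment (i) added to follow the August 2023 Investigator's Brochure (IB), has three rules. For Grade 2: "For Grade 2, withhold selpercatinib until resolution. Resume at next lower dose". For recurrence: "Discontinue selpercatinib for recurrent ILD/pneumonitis". Grade 3 or 4 events also end treatment. The Grade 2 rule names no starting dose and no floor.

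The general table in Section 6.6 gives adults three selpercatinib levels: 160, 120 and 80 mg BID (levels 1, -1 and -2). The adolescent table also ends at level -2, at 46 mg/m². For a patient already at the bottom, Section 6.6 says: "If previously receiving dose level -2, resume treatment at the same dose level". A second dose-modifying AE at that level ends treatment. On the number of steps it says: "Except as noted, a maximum of 2 dose level reductions will be allowed".

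Footnote a to the table reads: "Unless other specific dose reductions, as per Sections 6.6.1, 6.6.2, 6.6.3, and 6.6.4". Two other places in Section 6.6 point to the selpercatinib-specific rules: the bullet listing the toxicities with their own subsections, and the reference that follows the re-escalation rule. Both also stop at 6.6.4.

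**The concern.** Section 6.6.5 assumes that a lower dose exists. At 80 mg BID the general table has none, and the general rule for that level sends the patient back to the dose on which the event occurred. Nothing in Section 6.6 tells the site that 6.6.5 takes precedence.

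What is at stake is the handling of a lung toxicity whose recurrence ends treatment. Two sites reading the same protocol could dose the same patient differently, and one of them would do the opposite of what 6.6.5 intends.

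**Working it through.** The plan has no figure to reproduce here. The check applies both rules at each adult dose level for a first Grade 2 ILD event.

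| Dose at the event | Section 6.6.5 | General rule in Section 6.6 | Agree? |
|---|---|---|---|
| 160 mg BID (level 1) | 120 mg BID | 120 mg BID | Yes |
| 120 mg BID (level -1) | 80 mg BID | 80 mg BID | Yes |
| 80 mg BID (level -2) | A lower dose, not defined in the table | 80 mg BID | No |

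**The cap.** From 160 mg BID, the step to 120 is the first level and the step to 80 the second. Anything lower is a third, beyond the limit of two unless 6.6.5 counts as a noted exception. The lists of exceptions do not include it.

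**Where a lower dose appears.** For adults, 40 mg BID is used in 6.6.1 for hypersensitivity ("selpercatinib may be resumed at a reduced dose of 40 mg BID") and in 6.6.2 for liver tests. Neither section mentions ILD, and 6.6.5 refers to neither.

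**Daily dose under each outcome.**
- Same level, per Section 6.6: 2 × 80 = 160 mg/day.
- 40 mg BID, if borrowed from 6.6.1 or 6.6.2: 2 × 40 = 80 mg/day.
- Stop, if the cap is taken as binding: 0 mg/day.

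**How the sponsor handles the same step elsewhere.** Section 6.6.2 settles it for Grade 3 or higher liver tests: at 80 mg BID the site contacts the medical team, and at 40 mg BID it stops. Section 6.6.5 has no equivalent line.

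**Whether patients reach 80 mg BID.** There are three routes:
- two single-level reductions from 160 mg BID;
- one Grade 3 or higher liver event at 160 mg BID, after which 6.6.2 allows resumption two levels lower, directly at 80 mg BID, with at least 2 weeks there before escalation;
- stepwise escalation after hypersensitivity under 6.6.1, which passes through 80 mg BID "for a minimum of 7 days at each dose".

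Section 2.2.1 reports Grade 3 or higher ALT increase in 6.2% and AST increase in 4.7% of 422 patients, across tumour types and dose levels. So the liver route is not remote. These figures give neither the share of patients at 80 mg BID in this trial nor any rate of ILD.

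**The case against.** The strongest reply is that a specific rule overrides a general one, so 6.6.5 displaces the same-dose instruction. That is a fair reading, and probably the intended one. It still leaves the lower dose undefined, and the three cross-references do not include 6.6.5.

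Other text softens the problem:
- Section 8 requires immediate safety concerns to be discussed with the sponsor, and Section 7.1 lets the investigator stop treatment. These make harm less likely, but they name no dose and do not reconcile the two instructions.
- Section 6.6 calls its bullets guidelines that local practice may supersede. The same sentence goes on to name the local labels of the two control drugs. Whatever its reach for selpercatinib, it supplies no answer at 80 mg BID.
- Section 6.6 refers readers to the IB, and 6.6.5 was written from it. The IB may settle the matter. It is not among the documents reviewed, so that remains open.

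The scope is also limited. A patient who reached 80 mg BID because of earlier ILD stops under the recurrence rule. If ILD is the second dose-modifying AE at level -2, the general rule is to stop. Exclusion criterion 16 keeps out patients with an ILD diagnosis or symptoms at entry. All of this stands, and it makes the case narrow. It does not confine the case to patients reduced twice for other toxicities, because one liver event can lead directly to 80 mg BID.

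A reader might also infer that the reduction is undone at higher doses, since Section 6.6 says: "Re-escalation to a prior dose level after a dose reduction is permitted once the AE requiring dose reduction is resolved", and 6.6.5 withholds drug until resolution anyway. The documents do not support calling that a defect. The sentence permits re-escalation without requiring it, it applies to every AE, and Section 6.6.3 likewise sets no restriction of its own on re-escalation after thrombocytopenia. A ban on re-escalation after ILD would be a clinical preference with no source in the protocol.

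**Conclusion.** The conflict is real and confined to one step: a first Grade 2 ILD/pneumonitis event at dose level -2, 80 mg BID for adults. There, 6.6.5 orders a dose that Section 6.6 does not define, and Section 6.6 orders resumption at the dose on which the event occurred. A site following Section 6.6 would act contrary to 6.6.5.

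The size cannot be given. The documents report neither an ILD rate nor the share of patients at 80 mg BID. The conclusion rests on the protocol text alone and assumes that the IB does not already give a rule that sites apply.

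A reader might go further and infer an effect on treatment failure-free survival, because a toxicity stop counts only if it meets protocol guidance for discontinuation. The documents do not support a claim of any size. An independent committee decides this retrospectively on blinded data (Protocol Section 9.4.3.2.1), and no event rate is available. Power and alpha are not involved. Nor are the three possible outcomes equally supported: no text offers 40 mg BID for ILD, and it can only be inferred from other toxicities. This is a safety clarification, worth making because it is cheap.

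**What to change.** Add one sentence to Section 6.6.5, modelled on the tiers of 6.6.2 and checked against the current IB:

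*If Grade 2 ILD/pneumonitis occurs at 80 mg BID (or adolescent equivalent), do not resume at the same dose; discontinue selpercatinib unless the sponsor's medical team approves 40 mg BID; at 40 mg BID, discontinue.*

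Then add 6.6.5 to the three places in Section 6.6 that now stop at 6.6.4: the bullet listing selpercatinib-specific toxicities, the reference after the re-escalation rule, and footnote a to the dose table. If the IB has a different rule for this step, use that rule instead.

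The cost is one sentence and three section numbers in the next amendment, with the usual ethics approval under Section 10.1.1. It needs no new procedures, data or analyses.

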6.7. Intervention after the End of the Study

The end of study definition is defined in Section 4.4. Investigators will follow the schedule of activities provided in Section 1.3 until notified by Lilly that end of study has occurred.

6.7.1. Treatment after Study Completion

Study completion occurs after the clinical trial database is locked and final analysis of primary and secondary endpoints has been performed. Investigators will continue to follow SoAs (Section 1.3) for all patients until notified by Lilly that study completion has occurred.

6.7.1.1. Continued Access

Participants who are still on study intervention at the time of study completion may continue to receive study intervention if they are experiencing clinical benefit and no undue risks.

The continued access period will apply to this study only if at least 1 participant is still on study treatment when study completion occurs. Lilly will notify investigators when the continued access period begins.

Participants are not required to sign a new ICF before treatment is provided during the continued access period; the initial ICF for this study includes continued access under this protocol.

The participant's continued access to study intervention will end when a criterion for discontinuation is met (Section 7). Continued access follow-up will begin when the participant and the investigator agree to discontinue study intervention and lasts approximately 30 days. Follow-up procedures will be performed as shown in the Continued Access Schedule of Activities.

Participants who are in short-term follow-up when the continued access period begins will continue in short-term follow-up until the 30-day short-term follow-up visit is completed. Long-term follow-up does not apply.

Participants who are in long-term follow-up when the continued access period begins will be discontinued from long-term follow-up.

7. Discontinuation of Study Intervention and Participant Discontinuation/Withdrawal

7.1. Discontinuation of Study Intervention

Possible reasons leading to permanent discontinuation of investigational product:

- **Subject Decision**
 - the participant or the participant's designee, for example, parents or legal guardian requests to discontinue investigational product.

If a clinically significant finding is identified after enrollment, the investigator or qualified designee will determine if the participant can continue in the study and if any change in participant management is needed.

In addition, participants will be discontinued from the investigational product in the following circumstances:

- the patient becomes pregnant during the study. See Section 8.3 regarding regulatory reporting requirements on fetal outcome.
- the patient is significantly noncompliant with study procedures and/or treatment
- disease progression (radiographic or clinical progression). Patients with disease progression per investigator assessment may continue treatment while awaiting BICR confirmation of progression. Exceptions for continuing study treatment beyond suspected radiographic progression may be made on a case-by-case basis for patients who are believed to be clinically benefiting from study treatment, and the investigator and Lilly medical team agree that continuing study treatment is in the patient's best interest. Expectations for required study procedures and data collection for each patient will be made at the time of approval.
- the patient experiences unacceptable toxicity from study treatment
- the patient, for any reason, requires treatment with another therapeutic agent that has been demonstrated to be effective for treatment of the study indication. Discontinuation from study treatment will occur prior to introduction of the new agent
- the investigator decides that the patient should be discontinued from study treatment.

Participants discontinuing from the investigational product for any reason should complete AE and other follow-up procedures, including imaging assessments, per Section 1.3 (Schedule of Activities), Section 8.3 (Adverse Events and Serious Adverse Events), and Section 8.2 (Safety Assessments) of the protocol.

Participants assigned to treatment Arm B who experience progression may cross-over to selpercatinib after meeting criteria in Section 5.2.1 and comply with procedures noted in Section 1.3.

7.2. Participant Discontinuation/Withdrawal from the Study

Participants will be discontinued in the following circumstances:

- enrollment in any other clinical study involving an investigational product or enrollment in any other type of medical research judged not to be scientifically or medically compatible with this study
- participation in the study needs to be stopped for medical, safety, regulatory, or other reasons consistent with applicable laws, regulations, and Good Clinical Practices (GCP)
- subject decision
 - the participant or the patient's designee, for example, parents or legal guardian] requests to be withdrawn from the study.

Participants discontinuing from the study prematurely for any reason should complete AE and other safety follow-up per Section 1.3 (Schedule of Activities), Section 8.3 (Adverse Events and Serious Adverse Events), and Section 8.2 (Safety Assessments) of this protocol.

Participants discontinuing from study procedures may continue to be followed for survival, as long as they have not withdrawn consent for follow-up. If an in-person visit is not possible, survival status may be obtained by the site by contacting the patient directly via phone.

7.2.1. Discontinuation of Inadvertently Enrolled Patients

If the sponsor or investigator identify a participant who did not meet enrollment criteria and was inadvertently enrolled, then the patient should be discontinued from study treatment unless there are extenuating circumstances that make it medically necessary for the patient to continue on study treatment. If the investigator and the sponsor agree it is medically appropriate to continue, the investigator must obtain documented approval from the sponsor to allow the inadvertently enrolled participant to continue in the study with or without treatment with investigational product. Safety follow up is as outlined in Section 1.3 (Schedule of Activities), Section 8.3 (Adverse Events and Serious Adverse Events), and Section 8.2 (Safety Assessments) of the protocol.

For sites located in the United Kingdom (UK) and Germany, refer to Appendix 5 for country-specific discontinuation guidelines.

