8.1. Efficacy Assessments

8.1.1. Imaging

Efficacy assessments include tumor evaluation every 8 weeks after treatment initiation through week 24, and then every 12 weeks thereafter as noted in the SoA. Images are to be submitted for BICR evaluation within 5 days of completion. Patients who discontinue treatment without radiographic progression by BICR should continue to be assessed per the above schedule until radiographic disease progression is confirmed by BICR or death.

All patients are required to undergo neck, chest, abdomen, and pelvis imaging at baseline and subsequent serial imaging at disease assessment time points. All images will be collected at a central facility for central reviewer assessment during the study. Response will be assessed per RECIST 1.1 requirements (Eisenhauer et al., 2009).

Finally, all patients will enter Long-Term Follow-Up (LTFU) for confirming disease progression (if not occurring on treatment), subsequent anticancer therapy(ies), and survival.

Baseline disease assessment with radiographic tumor measurements using computed tomography (CT) or magnetic resonance imaging (MRI) of neck, chest, abdomen, and pelvis or any other areas with suspected disease involvement must be completed within 28 days of C1D1. MRI with contrast is the preferred imaging modality for imaging the abdomen and pelvis of subjects with

MTC given the inherent challenges in RECIST 1.1 assessment of MTC liver metastases. If MRI is not obtainable, triple phase CT of the abdomen (nonenhanced, arterial phase, and portal venous phase imaging) with pelvis is recommended. Routine single-phase CT of the abdomen and pelvis in the portal venous phase if the recommendations listed above are not obtainable. Brain imaging is required at baseline only for patients with a history of CNS metastases, or if clinically indicated and subsequent serial scans are required if brain metastases are present at baseline (MRI preferred, CT with contrast is acceptable if MRI contraindicated). Bone imaging is required at baseline only for patients with known bone metastases or if clinically indicated, and subsequent serial scans are required if bone metastases are present at baseline (MRI or CT with bone windows preferred).

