9.3. Populations for Analyses

For purposes of analysis, the following populations are defined:

| Population | Description |
|------------------------|---|
| Entered | All participants who sign informed consent for treatment |
| ITT/Enrolled | All randomized patients, even if a patient does not take the assigned treatment, does not receive the correct treatment, or otherwise does not follow the protocol. Patients will be analyzed according to the treatment group they were assigned to regardless of what actual treatment they receive. |
| Evaluable | Defined in specific subsections below, where applicable |
| Crossover | A subpopulation of patients included in the ITT population who were randomly assigned to Arm B, crossed over and took at least 1 dose of selpercatinib |
| Safety | All randomized participants who take at least 1 dose (including a partial dose) of study treatment. Analysis will be based on the actual treatment a participant received on the first study treatment administration, regardless of which treatment they were assigned to receive (“as treated”). |
| Tolerability Evaluable | All patients who were randomized prior to the interim efficacy analysis and received the first dose of study treatment at least 6 months prior to the data cutoff date. Analysis of tolerability will be based on the actual treatment a patient received on the first study treatment administration regardless of which treatment they were randomized to receive (“as treated”). |

Abbreviations: ITT = Intent to treat.

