10.5. Appendix 5: Country-specific Requirements

10.5.1. Discontinuation of Inadvertently Enrolled Patients in the UK and Germany

If the sponsor or investigator identifies a participant who did not meet enrollment criteria and was inadvertently enrolled, then the participant should be discontinued from study treatment and safety follow up should be performed as outlined in Section 1.3 (Schedule of Activities), Section 8.3 (Adverse Events and Serious Adverse Events), and Section 8.2 (Safety Assessments) of the protocol.

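### Section 7.2.1 makes off-treatment follow-up of randomized patients found ineligible subject to sponsor approval, which conflicts with Sections 4.1, 7.1 and 8.1.1 and permits arm-aware early censoring of PFS

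*Protocol*

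**What the plan says.** Protocol Section 7.2.1 covers enrolled patients later found not to have met the entry criteria; Section 9.3 equates enrolled with randomized. It is a subsection of 7.2, on leaving the study, not of 7.1, on stopping study drug.

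- **Study drug:** "then the patient should be discontinued from study treatment unless there are extenuating circumstances".
- **Staying in the study:** if investigator and sponsor agree that continuing is medically appropriate, "the investigator must obtain documented approval from the sponsor to allow the inadvertently enrolled participant to continue in the study with or without treatment".
- **Follow-up:** "Safety follow up is as outlined in Section 1.3 (Schedule of Activities), Section 8.3", and also Section 8.2.

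For the UK and Germany, Appendix 5 (Section 10.5.1) says "then the participant should be discontinued from study treatment and safety follow up should be performed as outlined in Section 1.3". It has no approval step and does not mention leaving the study.

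Other sections set general rules for patients who stop drug:

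- **Section 7.1:** "Participants discontinuing from the investigational product for any reason should complete AE and other follow-up procedures, including imaging assessments".
- **Section 8.1.1:** "Patients who discontinue treatment without radiographic progression by BICR should continue to be assessed per the above schedule", up to BICR-confirmed progression or death.
- **Section 4.1** (repeated in SAP Section 4.2): patients who stop for any reason except death, loss to follow-up or withdrawn consent are followed every 3 months for progression and later therapy, within survival follow-up.

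The efficacy analyses use the ITT set: "Patients will be analyzed according to the treatment group they were assigned to regardless of what actual treatment they receive".

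**The concern.** An ITT analysis needs outcomes after treatment stops as well as the patient's name in the analysis set. SAP Table JZJB.1 makes the same demand: stopping study drug before a PFS event is handled by treatment policy, so progression after stopping has to be observed.

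Section 7.2.1 puts a decision between the patient and that observation. The decision is made after randomization, in an open-label trial. Section 6.3 withholds aggregate unblinded data from the sponsor but does not hide the individual patient's arm from those deciding. If approval is sought or given differently by arm or by early clinical course, PFS and TFFS follow-up could end for reasons related to prognosis. Censoring would then be informative, and no method applied to the collected data can restore a progression that was never imaged.

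**Working it through.** **1. What the approval clause implies.** The first instruction in 7.2.1 stops study treatment and says nothing about leaving the study. The next makes remaining in the study subject to approval even for a patient off treatment. Approval to remain without treatment has a function only if an unapproved patient leaves. This is an inference, but it is the natural one, and the placement under 7.2 supports it.

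**2. Follow-up wording side by side.** Sections 7.1, 7.2 and 7.2.1 all point to Sections 1.3, 8.3 and 8.2.

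| Section | Follow-up it names |
|---|---|
| 7.1 (stopping drug) | AE and other procedures, imaging expressly included |
| 7.2 (leaving the study) | AE and other safety follow-up; survival follow-up permitted, not required |
| 7.2.1 (found ineligible) | Safety follow-up |
| Appendix 5 (UK, Germany) | Safety follow-up |

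A site could reasonably take the difference between the first row and the others as intended.

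**3. What the SAP does with a patient who leaves follow-up.** Under Table JZJB.3:

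- With no post-baseline scan and no known death, PFS is censored at randomization.
- A known death within two scan intervals of randomization is an event. The interval runs to the second scheduled scan plus 14 days, so about 2 × 8 + 2 = 18 weeks.
- A later death with no post-baseline scan is censored at randomization in the main analysis. Sensitivity analysis SA1 counts it as an event if it is known.
- With some scans done, PFS is censored at the last adequate assessment, unless a death becomes known before two scan intervals are missed.

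Table JZJB.7 treats TFFS in the same way, apart from toxicity events. OS is censored at the last date known alive. SA5 counts patients lost to follow-up as progressed, but Section 7.3 defines these as patients who repeatedly miss visits and cannot be contacted. A patient taken off by decision does not fit that definition.

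**4. Size.** The plan's event target reproduces. With HR 0.5, 1-sided alpha 0.025, 80% power and 2:1 allocation,

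d = (1.960 + 0.842)² / [(2/3)(1/3)(ln 0.5)²] = 7.85 / 0.1068 = 73.5, rounded up to 74; power at 74 events is 80.3%.

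The rate of inadvertent enrollment is not in the documents. Assume 1% to 5%, with none of these patients followed for efficacy:

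- Patients: 0.01 × 250 = 2.5 to 0.05 × 250 = 12.5, so about 3 to 13.
- PFS events unobserved, at 74/250 = 0.296 per patient: 0.7 to 3.7, so about 1 to 4.
- If the analysis ran short by that share of events: 73.3 events give 79.9% power and 70.3 events give 78.2%.

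The analysis is triggered by events, so in practice the loss would mostly delay it. Power is not the issue; who is censored, and why, is.

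**The case against.** A reader might infer that 7.2.1 takes ineligible patients off the study with safety follow-up alone and so removes them from the ITT comparison of PFS and OS. The documents do not support that.

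- The explicit default is to stop study treatment. Ineligibility is not named among the reasons in Section 7.2 for leaving the study. Nothing says that safety follow-up replaces all other follow-up, and the cited Section 1.3 is the full schedule, with imaging, survival and PFS2 assessments.
- ITT keeps every randomized patient as assigned. Only the per-protocol set, used for sensitivity analyses, excludes patients for deviations.
- Sections 4.1, 7.1 and 8.1.1 already require continued follow-up after drug is stopped. Section 7.3 seeks vital status for all randomized patients, including those never dosed.
- Appendix 5 leaves no approval discretion, so the arm-aware route does not exist in the UK or Germany.
- Progression and RET reports are reviewed before randomization (Section 4.1), which limits late discoveries on those criteria.

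All of this stands, and it reduces the point to a conflict between sections. It does not remove the conflict. A site handling an ineligible patient will turn to the specific section, and that section conditions off-treatment participation on approval. The vital-status provision belongs to the section on lost patients and recovers deaths, not progression. Late discoveries also remain possible, since central RET confirmation is retrospective (Section 5.1, criterion 4a).

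**Conclusion.** The point holds as an internal conflict with a consequence for primary-endpoint data. Followed literally, 7.2.1 lets a decision by people who may know the arm end imaging of a randomized patient and censor PFS and TFFS early, at randomization if there is no post-baseline scan and no early death. OS may be affected too. In Appendix 5 the fault is narrower: it is silent on efficacy follow-up.

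The effect is probably small. The 1 to 4 events rest on an assumed 1% to 5% rate and on every affected patient going unfollowed, which 4.1, 7.1 and 8.1.1 argue against. The direction of any bias cannot be stated. The case for acting is that the loss is avoidable and cannot be repaired at analysis.

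**What to change.** Reconcile Section 7.2.1 and Appendix 5 with Sections 4.1, 7.1 and 8.1.1 by separating study drug from follow-up:

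1. In both places, state that, whatever is decided about study drug, a randomized patient found ineligible remains in the study by default for scheduled BICR imaging and for subsequent-therapy, PFS2 and survival follow-up, unless consent is withdrawn.
2. In 7.2.1, state that the sponsor-approval condition does not apply to off-treatment follow-up.

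The rules on whether such a patient receives study drug are untouched. The cost is about two sentences in the protocol, plus a few extra scans and follow-up contacts in a handful of patients, most of which 8.1.1 already implies.
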